### Planned Analysis

- a) Table: summarize proportion and two-sided 90% confidence interval around the proportion of participants who have one of the defined AEs (EVW0206, EVW0207)
- b) Table: list of all events meeting the primary safety outcome definition (including weeks from start of study treatment, type of AE, grade, whether or not an SAE, whether or not it was a treatment limiting AE)

## 9 Secondary Outcome Measures Analyses

### 9.1 HCV RNA while on study treatment [V]

Note: A figure showing each participant's  $\log_{10}$  HCV RNA trajectory including on-treatment and post-treatment periods will be included. An appendix to the report will be included listing scheduled measurement weeks, calculated weeks of each measurement, HCV RNA value,  $\log_{10}$  HCV RNA value, and reason for any missed measurement.

Secondary Outcome Measure (from protocol section 9.2.2.1)

HCV RNA undetectable (<LLOQ TND) at 1, 2, 4, and 8 weeks after starting study treatment. Measurements will be assigned to these times within windows of 4 to 10, 11 to 17, 21 to 42, and 49 to 70 days, inclusive, respectively. If there is more than one measurement within a window, then the measurement closest to the targeted time will be used. If there is no measurement within a window, then the participant will be considered as having detectable HCV RNA at the targeted time, unless both the preceding and succeeding measurements are undetectable (<LLOQ TND).

Planned Analysis

- a) Table: summarize the proportion of HCV undetectable (<LLOQ TND) of the assay at 1, 2, 4, 8 weeks after starting study treatment. A 90% two-sided confidence interval will be provided around the observed proportions (HCVRNALDMS)

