## 2 Study Overview

### 2.1 Study Schema

#### (Extracted from Protocol Version 2.0)

#### DESIGN

SWIFT-C is a Phase I, open-label, two-cohort clinical trial, in which between 44 and 50 acutely HCV-infected HIV-1 positive participants will be enrolled and administered oral sofosbuvir (SOF) in combination with weight-based ribavirin (RBV, cohort 1) or ledipasvir (LDV, cohort 2).

The study will investigate the safety and efficacy of two SOF-containing regimens and will assess if the addition of a second DAA allows for a shortened course of therapy. The study will open the first cohort with sofosbuvir plus ribavirin (SOF+RBV) for 12 weeks and with a planned accrual of at least 17 participants. The second cohort will open with ledipasvir/sofosbuvir (LDV/SOF) for an 8-week treatment. The second cohort will include at least 27 participants. Each cohort will occur in two steps: on treatment (Step 1) and followup (Step 2). The cohorts will enroll sequentially.

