## 2.5 Visit and Evaluation Schedule

The Cohort 2 expected schedule for on-treatment clinic visits is shown in Table 1 and the expected schedule for post-treatment follow up clinic visits is shown in Table 2 below. Unless otherwise noted, analyses by A5327 study week will utilize these study week definitions (defined in days); the start time for calculation of study week will be the date of first dose of treatment.

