### 9.2 HCV RNA during follow-up [V]

Secondary Outcome Measure (from protocol section 9.2.2.2)

HCV RNA undetectable (<LLOQ TND) at 2 (SVR2), 4 (SVR4), 8 (SVR8), and 24 (SVR24) weeks after last dose of study treatment. The windows for these measurements will be 9 to 22, 23 to 50, 51 to 78, and 161 days onwards. If there is more than one measurement within a window, then the measurement closest to the targeted time will be used. If there is no measurement within a window, then the participant will be considered as having detectable HCV RNA at the targeted time, unless (for weeks 4 and 8) the preceding and subsequent HCV RNA measurements are both <LLOQ TND.

Planned Analysis

Note: For clarity of presentation, results for the primary outcome measure (SVR12) will be included in the following tables.

- a) Table: summarize the proportion of HCV undetectable (<LLOQ TND) of the assay at 2 (SVR2), 4 (SVR4), 8 (SVR8), 12 (SVR12) and 24 (SVR24) weeks after last dose of study treatment. A 90% two-sided confidence interval will be provided around the observed proportions (HCVRNALDMS)
- b) Figure: summarize the proportion of HCV undetectable, with the upper and lower limit of the confidence interval at 2 (SVR2), 4 (SVR4), 8 (SVR8), 12 (SVR12) and 24 (SVR24) weeks after last dose of study treatment (HCVRNALDMS).

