### 9.3 HCV RNA Relapse [V]

#### Secondary Outcome Measure (from protocol section 9.2.2.3)

To evaluate virologic evidence of relapse, defined as HCV RNA undetectable (<LLOQ TND) at end-of-treatment but HCV RNA quantifiable ( $\geq$ LLOQ) during followup, will require confirmation and should be performed as soon as possible but within 2 weeks after determination of initial observation.

For analysis purposes, confirmatory values obtained after 2 weeks will be included.

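### The on-treatment week 8 HCV RNA window runs past the end of treatment and overlaps the SVR2 window, so one sample can count for both outcomes

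*SAP*

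**What the plan says.** The SAP's Design paragraph (section 2.1) describes Cohort 2 as receiving "ledipasvir/sofosbuvir (LDV/SOF) for an 8-week treatment". Section 2.5 introduces Table 1 as the schedule of on-treatment visits and says that "the start time for calculation of study week will be the date of first dose of treatment". Table 1 gives days 49-70 for week 8. Section 9.1, headed "HCV RNA while on study treatment", repeats this: the week 4 and week 8 windows are "21 to 42, and 49 to 70 days, inclusive, respectively".

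If a window holds several samples, "then the measurement closest to the targeted time will be used". If it holds none, the participant is scored detectable, "unless both the preceding and succeeding measurements are undetectable (<LLOQ TND").

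Post-treatment windows run on a different clock, from the last dose. Section 9.2 states: "The windows for these measurements will be 9 to 22, 23 to 50, 51 to 78, and 161 days onwards". The first of these is SVR2.

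No section requires that a sample assigned to an on-treatment week be taken on treatment, or says that a sample may be used only once.

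**The concern.** Within Table 1 the windows do not overlap, and the same is true within Table 2. The overlap appears only when the two clocks are put on one axis. Week 8 has the same allowance as week 4, 7 days before to 14 days after target. For someone completing 8 weeks, those 14 days fall after treatment has ended.

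Two things follow. A sample taken at an on-time SVR2 visit satisfies the week 8 window as well, so it can count twice. And when no closer sample exists, an off-treatment value is reported as an observed on-treatment result, and the missing-data rule is never reached. At stake is the accuracy of a secondary on-treatment proportion in a cohort with a planned minimum of 27.

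**Working it through.** **Inputs.** Treatment of 8 weeks = 56 days (section 2.1). Day 0 is the first dose (section 2.5, Table 1). Week 8 window 49-70 (Table 1, section 9.1). SVR2 window: last dose + 9 to + 22 (Table 2, section 9.2). Cohort 2 minimum of 27 (section 2.1, Sample Size). Assumption: the last planned dose is on day 55 (56 daily doses from day 0) or day 56; both are shown.

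**1. The plan's own windows.** Target - 7 to target + 14: week 4 is 28 - 7 = 21 to 28 + 14 = 42; week 8 is 56 - 7 = 49 to 56 + 14 = 70. Both are reproduced. The week 8 window is 22 days long.

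**2. Week 8 against SVR2, in days from first dose.**

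| | Last dose day 55 | Last dose day 56 |
|---|---|---|
| Days of week 8 window after last dose | 70 - 55 = 15 | 70 - 56 = 14 |
| SVR2 window | 64-77 | 65-78 |
| Overlap with 49-70 | 64-70, 7 days | 65-70, 6 days |
| On-time SVR2 visit (last dose + 14) | 69 | 70 |

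The on-time SVR2 visit lies inside the week 8 window in both columns.

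**3. On-schedule completer with a week 8 sample.** An on-treatment sample from day 49 onward is at most 56 - 49 = 7 days from target. The earliest SVR2-window sample is 64 - 56 = 8 or 65 - 56 = 9 days away. It never displaces the on-treatment sample.

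**4. Completer with week 8 missed and the SVR2 sample inside days 49-70.** As written, the SVR2 sample is the week 8 result. If it were excluded, the missing-data rule would apply, with week 4 as the preceding and SVR2 as the succeeding measurement.

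| Week 4 | SVR2 | Week 8 as written | Week 8 if SVR2 sample excluded |
|---|---|---|---|
| undetectable | undetectable | undetectable | undetectable |
| undetectable | detectable | detectable | detectable |
| detectable | undetectable | **undetectable** | **detectable** |
| detectable | detectable | detectable | detectable |

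Only the third row changes.

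**5. Early stopping.** Take the last dose and last on-treatment sample on day 49, which is 7 days from target. The SVR2 window is 49 + 9 = 58 to 49 + 22 = 71. A follow-up sample on days 58-62 is 2 to 6 days from day 56, so it displaces the day 49 sample. If the two results differ, the week 8 score changes, in either direction. With last dose on day 42, the on-time SVR2 visit is 42 + 14 = day 56, exactly the week 8 target. If no other sample is in the window, the table in step 4 applies, with the last on-treatment sample in place of week 4.

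**6. Size.** One changed score is 1/27 = 3.7 percentage points of the week 8 proportion at the minimum cohort size, and less in a larger cohort.

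**7. Check of a cap at 8 days after last dose.** For completers the week 8 window would end on day 55 + 8 = 63 or 56 + 8 = 64, one day before SVR2 opens, so the overlap is 0. In the day 49 example it would end on day 57, and the day 49 sample would stand.

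**The case against.** The strongest reply is that little changes in practice. The closest-to-target rule already handles the ordinary participant (step 3), and three of the four missed-visit patterns score the same either way (step 4). In the fourth, the present rule is arguably nearer the truth, since a participant undetectable about two weeks off drug had probably cleared virus by end of treatment. Section 9.1 also words the outcome as time since starting treatment, which could mean regardless of treatment status; early stoppers' follow-up samples would then belong at week 8 by design. The section also calls for individual trajectories and a listing of every measurement with its calculated week, so a reader could trace each sample. All of this limits the size of the problem. It does not settle which reading applies: the heading of section 9.1 and the introduction to Table 1 both point to on-treatment samples, and nothing bars double use.

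A reader might also infer that an early relapse is misreported as on-treatment failure and lost from the relapse listing. The documents do not support that. For a missed week 8 visit with relapse by post-treatment week 2, the missing-data rule gives detectable as well, because the succeeding measurement is detectable. Section 9.3 has relapse "defined as HCV RNA undetectable (<LLOQ TND) at end-of-treatment" but does not equate that time with week 8, and Table 2 has its own Week 0 on the last day of treatment. Nor does every misassigned sample move the proportion by 3.7 points; it moves only when the score differs.

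**Conclusion.** The point holds as a limited defect in a secondary outcome. The window runs 14 to 15 days past planned last dose, overlaps SVR2 by 6 to 7 days, and permits both double use and an off-treatment value reported as on-treatment. The score changes in two settings only: a missed week 8 visit with week 4 detectable and SVR2 undetectable, and early stopping where a follow-up sample with a different result lies nearer day 56 than the last on-treatment sample. Each case moves the week 8 proportion by up to 3.7 points. How many participants are in either setting cannot be told from the SAP. SVR12, at 79-112 days after last dose, is unaffected. The conclusion rests on a last planned dose on day 55 or 56, and on reading section 9.1 as its heading says.

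**What to change.** In Table 1 (as a footnote) and section 9.1, add: a sample taken more than 8 days after the last dose may not be assigned to an on-treatment week, and no sample may be assigned to both an on-treatment and a post-treatment time point. Where no eligible sample remains, the existing missing-data rule applies. State that a follow-up sample may still act as the succeeding measurement in that rule, so that the bar on double use does not disable it.

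A strict cut at the last dose is not advised. With the last dose on day 55, it would discard an on-time day 56 sample. The price of the 8-day allowance is that a sample taken shortly after last dose can still be chosen over an earlier on-treatment one (day 58 over day 49, for a completer).

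The cost is a short addition to section 9.1, a footnote and one programming condition. The downside is that a few more week 8 values will be handled by the missing-data rule. Sections 9.6 and 9.7 take their windows from the HCV RNA rules, so the text should say whether the condition applies there too.

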### 9.2 HCV RNA during follow-up [V]

Secondary Outcome Measure (from protocol section 9.2.2.2)

HCV RNA undetectable (<LLOQ TND) at 2 (SVR2), 4 (SVR4), 8 (SVR8), and 24 (SVR24) weeks after last dose of study treatment. The windows for these measurements will be 9 to 22, 23 to 50, 51 to 78, and 161 days onwards. If there is more than one measurement within a window, then the measurement closest to the targeted time will be used. If there is no measurement within a window, then the participant will be considered as having detectable HCV RNA at the targeted time, unless (for weeks 4 and 8) the preceding and subsequent HCV RNA measurements are both <LLOQ TND.

Planned Analysis

Note: For clarity of presentation, results for the primary outcome measure (SVR12) will be included in the following tables.

- a) Table: summarize the proportion of HCV undetectable (<LLOQ TND) of the assay at 2 (SVR2), 4 (SVR4), 8 (SVR8), 12 (SVR12) and 24 (SVR24) weeks after last dose of study treatment. A 90% two-sided confidence interval will be provided around the observed proportions (HCVRNALDMS)
- b) Figure: summarize the proportion of HCV undetectable, with the upper and lower limit of the confidence interval at 2 (SVR2), 4 (SVR4), 8 (SVR8), 12 (SVR12) and 24 (SVR24) weeks after last dose of study treatment (HCVRNALDMS).

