**Table 2: Weeks Since Starting Post-Treatment Follow up**

	Week 0	Week 2	Week 4	Week 8	Week 12	Week 24
Days	Last day of treatment	9-22	23-49	51-78	79-112	161 onwards

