## 8 Primary Endpoint Analyses

### 8.1 Efficacy Outcome [IP]

Note: For clarity of presentation, results for the primary efficacy outcome and for the secondary efficacy outcomes concerning HCV RNA will be presented together in the analysis report.

Primary Outcome Measure (from protocol section 9.2.1.1)

SVR12 is defined as HCV RNA undetectable (<LLOQ TND) of the assay at 12 weeks after date of last dose of study treatment.

The 12 week measurement will be the measurement obtained closest to 84 days (i.e. 12\*7 days), within the window 79 to 112 days inclusive after study treatment discontinuation. This analysis will be intent to treat (ITT) analysis.

If a participant has no HCV RNA measurement within this window, then the participant will be considered as having detectable HCV RNA at 12 weeks unless the preceding and subsequent HCV RNA measurements are both undetectable (<LLOQ TND).

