#### Planned Analysis

- a) List: Participants who have virologic evidence of relapse. The listing will include week of HCV RNA undetectable (<LLOQ TND), HCV RNA undetectable at end of study treatment, post treatment week of HCV RNA detectable ( $\geq$ LLOQ) and confirmation of HCV RNA detectability (HCVRNALDMS)

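### Section 9.2 scores a missed post-treatment week 2 HCV RNA as detectable even between two undetectable values, so SVR2 follows a stricter rule than SVR4, SVR8 and SVR12 (SVR12 itself is unaffected)

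*SAP*

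**What the plan says.** Three sections of the SAP say how a missing HCV RNA value is scored. Each starts from missing counts as detectable and then allows an exception when the values on either side are undetectable.

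- **8.1 (SVR12, primary):** detectable "unless the preceding and subsequent HCV RNA measurements are both undetectable (<LLOQ TND".
- **9.1 (on-treatment weeks 1, 2, 4 and 8):** detectable "unless both the preceding and succeeding measurements are undetectable (<LLOQ TND". No week is excluded.
- **9.2 (post-treatment weeks 2, 4, 8 and 24):** detectable "at the targeted time, unless (for weeks 4 and 8) the preceding and subsequent HCV RNA measurements are both <LLOQ TND". Weeks 2 and 24 get no exception, and no reason is given.

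The SAP relies on an end-of-treatment result elsewhere. Section 9.3 defines relapse from "HCV RNA undetectable (<LLOQ TND) at end-of-treatment", and its listing includes "HCV RNA undetectable at end of study treatment". Table 2 also has a follow-up Week 0, labelled "Last day of treatment".

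Section 9.2 puts SVR2, SVR4, SVR8, SVR12 and SVR24 in one table and one figure; the figure is to "summarize the proportion of HCV undetectable, with the upper and lower limit of the confidence interval" at each of these times.

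**The concern.** Leaving out week 24 is understandable: its window is open-ended from day 161, so normally no later sample exists to close the bracket. Week 2 is different, because it has a measurement before it and week 4 after it.

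The consequence is that SVR2 is scored on a stricter rule than its neighbours in the same table and figure. A missed week 2 visit, with no virological event behind it, lowers SVR2. The response curve can then appear to rise from SVR2 to SVR4, purely because of scoring.

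The appendix in 9.1, which gives the "reason for any missed measurement", lets a reader trace individual misses. It does not correct the proportions or intervals that will be read and quoted.

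**Working it through.** **The rule at each time point**

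| Time point | Values on both sides possible? | Exception granted? |
|---|---|---|
| On-treatment week 1 | Yes, but the preceding value is baseline | Yes (9.1), nearly empty |
| On-treatment weeks 2, 4, 8 | Yes | Yes (9.1) |
| Post-treatment week 2 | Yes | **No (9.2)** |
| Post-treatment weeks 4, 8 | Yes | Yes (9.2) |
| Post-treatment week 12 | Yes | Yes (8.1) |
| Post-treatment week 24 | Normally no later sample | No (9.2) |

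**Same participant, same two samples.** Suppose post-treatment weeks 2 and 4 are both missing, and end of treatment and week 8 are both undetectable. Section 9.2 speaks of preceding and subsequent measurements, so the measurement preceding week 4 is the end-of-treatment value. SVR4 is then scored undetectable and SVR2 detectable.

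**Effect per miss.** The SAP has no figure of its own to reproduce here. The input is n = 27, the Cohort 2 minimum in the sample size section. Everyone is taken to be truly undetectable. The 90% intervals are exact Clopper-Pearson, as an illustration, because 9.2 names no interval method.

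| Week 2 misses | SVR2 as written | 90% CI |
|---|---|---|
| 0 | 27/27 = 100% | 89.5-100 |
| 1 | 26/27 = 96.3% | 83.6-99.8 |
| 2 | 25/27 = 92.6% | 78.5-98.7 |

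With week 2 bracketed, all three rows would read 27/27, provided the values on either side are undetectable.

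**Expected size.** The SAP gives no missed-visit rate, so I assume independent misses with probability p = 2%, 5% or 10% per visit.

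The chance of at least one missed week 2 among 27 is 1 - (1 - p)^27 = 42%, 75%, 94%. Under the present rule the expected SVR2 loss is p. The SVR4 loss depends on how the bracket is read.

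- *Adjacent visits* (a missing neighbouring visit blocks the bracket): SVR4 loss = p[1 - (1 - p)^2]. The rise from SVR2 to SVR4 = p - p[1 - (1 - p)^2] = p(1 - p)^2. With the fix, SVR2 and SVR4 have the same expected loss, so the rise is 0.
- *Nearest actual measurements:* SVR4 is lost when week 4, week 2 and end of treatment are all missing, about p^3. The rise is about p - p^3. With the fix, SVR2 is lost when week 2 and end of treatment are both missing, about p^2, leaving a rise of about p^2 - p^3. This treats any earlier on-treatment value as not undetectable and assumes some later sample exists.

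| p | Rise now, adjacent visits | Rise now, nearest measurements | Rise after fix |
|---|---|---|---|
| 2% | 1.9 points | 2.0 points | 0 to 0.04 |
| 5% | 4.5 points | 5.0 points | 0 to 0.24 |
| 10% | 8.1 points | 9.9 points | 0 to 0.9 |

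**The case against.** The strongest defence is that the exclusion is deliberate. It is written as an explicit parenthesis, and nothing in the SAP promises one rule for all time points. Week 2 is the first off-treatment time point, so the value before it is taken on drug or at end of treatment, and insisting on an observed value there is conservative. Section 9.1 does bracket across the end of treatment at on-treatment week 8, but in the other direction: a later off-drug value supports an on-drug time point. The exclusion may also come from protocol section 9.2.2.2, which 9.2 cites. Finally, relaxing a conservative rule in the regimen's favour after all participants had completed treatment (Introduction) calls for care.

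Much of this stands. The rule is explicit, conservative, secondary and possibly inherited from the protocol, and the timing limits how a change should be reported. The on-drug argument does not rescue it. In a week 2 bracket, the evidence against relapse is the later, off-drug undetectable value, and 9.2 already lets an end-of-treatment value precede week 4 when week 2 is missing.

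The comparison with other time points should not be overstated either. Week 1 formally has the exception, but its preceding value is baseline, which is undetectable only in the unusual case of spontaneous clearance noted in section 5. The Week 0 entry in Table 2 defines a follow-up time and does not by itself show that an HCV RNA sample is planned. The support for a preceding value is on-treatment week 8 and the relapse definition in 9.3.

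**Conclusion.** The point holds and is minor. SVR2 is scored differently from SVR4, SVR8 and SVR12 beside it, without a stated reason. The bias runs one way, against the regimen, at 3.7 points per affected participant when n = 27. The expected rise is conditional on the assumed miss rates, on independence, and on everyone being truly undetectable; its range reflects an ambiguity in what counts as a neighbouring measurement.

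A reader might infer three stronger things that the document does not support:

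- *That the primary result is at risk.* It is not. SVR12 has its own rule in 8.1, which includes the exception.
- *That 9.2 is contradictory or cannot be applied.* It can be applied exactly as written; the fault is an unexplained departure from the SAP's own approach.
- *That adding week 2 removes the artefact entirely.* That is so only on the adjacent-visit reading, which the text does not state. On the nearest-measurement reading a small residue remains.

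**What to change.** In 9.2, extend the parenthesis so that the exception covers weeks 2, 4 and 8. State that for week 2 the preceding measurement is the last HCV RNA measurement before its window, as for the other brackets. No special day limit is needed, since no other bracket has one.

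Because all participants had completed treatment when the SAP was prepared, footnote SVR2 under the present rule wherever it differs. If protocol section 9.2.2.2 sets the exclusion, document the departure.

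The cost is a few words in 9.2, a footnote and a few lines in the hcvrna derivation; no new data are needed. The downside is that a transient rebound at week 2 between two undetectable values would be missed, a risk 9.2 already accepts at weeks 4 and 8.

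As an editorial correction only: Table 2 ends the post-treatment week 4 window at day 49, and 9.2 ends it at day 50. Section 2.5 lets a later section override its tables, so 9.2 governs and no HCV RNA result changes, but the two should match.
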